## **2.8 PHARMACOKINETIC/PHARMACODYNAMIC ENDPOINTS**

Pharmacokinetic concentrations collected during the 12-week Efficacy Period will be used for population PK analysis and PK/PD analysis.

## 3.0 STUDY DESCRIPTION

### 3.1 STUDY DESIGN

This is a Phase 3, multi-center, randomized, double-blind study to confirm the efficacy and safety of K-877 0.2 mg twice daily compared to matching placebo (in the 12-week Efficacy Period) and an active comparator, fenofibrate (in the 40-week Extension Period), in patients with fasting TG levels  $\geq 500$  mg/dL (5.65 mmol/L) and  $< 2000$  mg/dL (22.60 mmol/L) and normal renal function.

Eligible patients will enter a 4- to 6-week lifestyle stabilization period (4-week stabilization for patients not requiring washout and 6-week washout and stabilization for patients on lipid-altering therapy other than statins, ezetimibe, or proprotein convertase subtilisin/kexin type 9 [PCSK9] inhibitors). The stabilization period will be followed by a 2-week TG qualifying period (Visits 2 [Week -2] and 3 [Week -1]), and patient eligibility will be assessed based on the mean TG value from these 2 visits. If the patient's mean TG level during the TG qualifying period is  $\geq 450$  mg/dL (5.09 mmol/L) and  $< 500$  mg/dL (5.65 mmol/L), an additional TG measurement can be taken 1 week later at Visit 3.1. The mean of all 3 TG measurements will be used to determine eligibility for the study. After confirmation of qualifying fasting TG values, eligible patients will enter a 12-week, randomized, double-blind Efficacy Period. At Visit 4 (Day 1), patients will be randomly assigned in a 2:1 ratio to K-877 0.2 mg twice daily or identical matching placebo tablets twice daily. During the 12-week Efficacy Period, patients will return to the site at Visit 5 (Week 4), Visit 6 (Week 8), and Visit 7 (Week 12) for efficacy and safety evaluations.

Patients who successfully complete the 12-week Efficacy Period are eligible to continue in a 40-week, double-blind, active-controlled Extension Period after completing the Visit 7 (Week 12) procedures. Patients randomized to receive K-877 0.2 mg twice daily in the 12-week Efficacy Period will continue to receive K-877 0.2 mg twice daily, as well as placebo matching fenofibrate 145 mg once daily, in the 40-week Extension Period. Patients randomized to receive placebo matching K-877 0.2 mg twice daily in the 12-week Efficacy Period will receive fenofibrate 145 mg once daily and placebo matching K-877 0.2 mg twice daily in the 40-week Extension Period.

From Visit 7 (Week 12), patients not on statins, ezetimibe, or PCSK9 inhibitors may initiate therapy, and patients receiving statins, ezetimibe, or PCSK9 inhibitors may alter their dose, as indicated by guidelines or local standard of care.

After Visit 8 (Week 16), patients are to return to the site every 12 weeks until the last visit (Visit 11 [Week 52]).

Table 2 presents the clinical evaluation schedule performed during the study.

**Table 2: Clinical Evaluation Schedule**

ASSESSMENTS PERFORMED	STUDY PERIOD									
	Screening Period		Treatment Period							
	Lifestyle Stabilization/ Washout Period	Triglyceride Qualifying Period [1]	12-Week Efficacy Period				40-Week Extension Period [2]			
Time	Week -8 or -6	Week -2 ±3 days	Week -1 ±3 days	Day 1	Week 4 ±3 days	Week 8 ±3 days	Week 12 ±3 days	Week 16 ±3 days	Week 28 ±7 days	Week 40 ±7 days
Visit Number	1 [3]	2	3 [1]	4	5	6	7	8	9	10
Informed consent	X									
Medical, surgical, and family history, and demographics	X									
Concomitant medication(s)	X	X	X	X	X	X	X	X	X	X
Inclusion/exclusion criteria	X	X	X	X						
Vital signs (heart rate, respiratory rate, and blood pressure)	X	X	X	X	X	X	X	X	X	X
Height [4], weight, and waist circumference	X			X			X			X
Register screening number with IRT	X									
Urine drug and blood alcohol screen [5]	X									
[REDACTED]										
[REDACTED]										
[REDACTED]										
Amylase and lipase	X			X						
HbA 1c	X			X			X		X	X
Insulin, glycated albumin, HOMA-IR, HOMA- $\beta$ , and QUICKI				X			X		X	X
Serum pregnancy test for WOCBP	X									
Urine pregnancy test for WOCBP				X			X		X	X
Chemistry, hematology, coagulation, and urinalysis	X			X	X		X	X	X	X
Plasma Population PK sampling [8]										
PK/PD sampling [9]										
TG, TC, HDL-C, non-HDL-C, LDL-C, and remnant cholesterol [10]	X	X	X	X	X	X	X	X	X	X

\*footnotes on following page

**Table 2: Clinical Evaluation Schedule (Continued)**

**Table 2: Clinical Evaluation Schedule (Continued)**

## 4.0 PATIENT ELIGIBILITY AND WITHDRAWAL CRITERIA

### 4.1 INCLUSION CRITERIA

Patients who meet all of the following criteria will be eligible to participate in the study:

1. Able to understand and willing to comply with all study requirements and procedures throughout the duration of the study and give written informed consent;
2. Aged  $\geq 18$  years;
3. Patients receiving moderate- or high-intensity statin therapy must meet one of the following criteria unless they have any exceptional conditions (see inclusion criterion 4):
  - a. Aged  $\geq 21$  years with clinical atherosclerotic cardiovascular disease (ASCVD) (history of acute coronary syndrome or myocardial infarction, stable or unstable angina, coronary or other arterial revascularization, stroke, transient ischemic attack [TIA] presumed to be of atherosclerotic origin, or peripheral arterial disease or revascularization), on a high-intensity statin (or moderate-intensity statin if not a candidate for high-intensity statin due to safety concerns – including, but not limited to, examples in Appendix Table B3);
  - b. Aged  $\geq 21$  years with a history of LDL-C  $\geq 190$  mg/dL, which is not due to secondary modifiable causes, on a high-intensity statin (or moderate intensity statin if not a candidate for high-intensity statin due to safety concerns – including, but not limited to, examples in Appendix Table B3);
  - c. Aged 40 to 75 years, inclusive, without clinical ASCVD but with diabetes and a history of LDL C of 70 to 189 mg/dL, inclusive, on a moderate- or high-intensity statin; or
  - d. Aged 40 to 75 years, inclusive, without clinical ASCVD or diabetes, with a history of LDL-C of 70 to 189 mg/dL, inclusive, with estimated 10-year risk for ASCVD of  $\geq 7.5\%$  by the Pooled Cohort Equation (see Appendix C) on a moderate- or high-intensity statin;
4. Patients currently on a low-intensity statin or not on a statin, must meet one of the following criteria:
  - a. Patient does not meet any criteria for moderate- or high-intensity statin therapy listed above (see inclusion criteria 3.a. through 3.d.);
  - b. Patient does meet one or more criteria for moderate- or high-intensity statin therapy listed above (see inclusion criteria 3.a. through 3.d.); but the patient is not a candidate for moderate- or high-intensity statin due to safety concerns (including, but not limited to, examples in Appendix B), or due to partial or complete statin intolerance;

c. Patient does meet one or more criteria for moderate- or high-intensity statin therapy listed above (see inclusion criteria 3.b. through 3.d., except for 3.a.); but the patient is not a candidate for moderate- or high-intensity statin for primary prevention after considering individual risk evaluation (e.g., current LDL-C  $\leq$ 70mg/dL) and patient preference (see Appendix B);

Topic	Percentage
Smart cities	95
Smart homes	92
Smart transportation	90
Smart energy	88
Smart waste management	85
Smart agriculture	82
Smart healthcare	80
Smart water management	78
The concept of a 'smart city'	70

## 4.2 EXCLUSION CRITERIA

Patients who meet any of the following criteria will be excluded from participation in the study:

1. Patients who will require lipid-altering treatments other than study drugs (K-877 or fenofibrate), statins, ezetimibe, or PCSK9 inhibitors during the course of the study. These include bile acid sequestrants, non-study fibrates, niacin ( $>100$  mg/day), omega-3 fatty acids ( $>1000$  mg/day), or any supplements used to alter lipid metabolism including, but not limited to, red rice yeast supplements, garlic supplements, soy isoflavone supplements, sterol/stanol products, or policosanols;
2. Body mass index (BMI)  $>45$  kg/m^2 at Visit 1 (Week -8 or Week -6);
3. Patients with type 1 diabetes mellitus;
4. Patients with newly diagnosed (within 3 months prior to Visit 2 [Week -2]) or poorly controlled type 2 diabetes mellitus (T2DM), defined as hemoglobin A1c (HbA1c)  $>9.5\%$  at Visit 1 (Week -8 or Week -6);

A large block of black redacted text, consisting of approximately 20 lines of text, each represented by a horizontal black bar. The text is completely obscured, and no individual words or characters can be identified.

A series of horizontal black bars of varying lengths, likely representing data points or measurements. The bars are arranged in a grid-like pattern with some vertical alignment. Some bars have small black squares at their left ends.

### **4.3 STUDY DRUG DISCONTINUATION CRITERIA**

It will be necessary to make a distinction between patients who prematurely discontinue study drug treatment and those who withdraw from the study for any reason.

If the patient discontinues study drug, the reason should be captured and could include the following:

1. The patient requests discontinuation of the study drug;
2. The patient begins to take any medication(s) that is contraindicated by the protocol;
3. The patient develops an AE that, in the opinion of the Investigator, would compromise the patient's safety to continue the study drug;
4. The patient meets any of the criteria specified in Section 4.6;
5. A female patient becomes pregnant during the study;
6. In the Investigator's judgment, it is in the patient's best interests; or
7. The patient is unblinded.

During the 12-week Efficacy Period, patients who discontinue study drug prematurely will remain in the study until Visit 7 (Week 12). However, patients who discontinue study drug during the 40-week Extension Period will be required to withdraw from the study and requested to complete the full panel of assessments scheduled for the Early Termination (ET) Visit (see Section 4.4). If a patient who has discontinued study drug fails to attend any follow-up appointments, reasonable efforts (telephone calls to family members or friends, e-mail contacts, etc.) will be made in order to encourage the patient to complete the study visits.

Although a patient is not obligated to give his/her reason for discontinuing study drug, the Investigator will make a reasonable effort to obtain the reason while fully respecting the patient's rights. The reason for discontinuation of study drug must be documented in the electronic case report form (eCRF). The Clinical Study Report (CSR) will include the reason(s) for discontinuation of study drug.

Patients will not be allowed to restart the study drug in the event of discontinuation; however, study drug may be restarted in cases of study drug interruption due to temporary use of prohibited medication(s) and AEs.

#### 4.4 WITHDRAWAL CRITERIA

The patient has the right to withdraw from the study at any time. Nevertheless, in this study, every attempt will be made to prevent missing data and to obtain complete follow-up of all patients during the 12-week Efficacy Period. Investigators will be trained to minimize full withdrawals from the 12-week Efficacy Period wherever possible. Patients who discontinue study drug during the first 12 weeks are not required to withdraw from the study. These patients will be encouraged to remain in the study and asked to conduct the remaining study visits as outlined in the protocol through Visit 7 (Week 12). At a minimum, measurements of lipid parameters at key time points, particularly Visit 7 (Week 12), should be taken for all study patients, regardless of adherence to therapy or study protocol. If a patient fails to actively maintain contact with the Investigator, reasonable efforts (telephone calls to family members or friends, e-mail contacts, etc.) will be made in order to encourage the patient to complete the study visits.

If the patient withdraws from the study, the reason should be captured and could include the following:

1. The patient withdraws consent at any time or requests discontinuation of the study drug during the 40-week Extension Period;
2. The patient begins to take any medication(s) during the 40-week Extension Period that is prohibited by the protocol;
3. The patient develops an AE that, in the opinion of the Investigator, would compromise the patient's safety by continuing in the study;
4. The patient meets any of the criteria specified in Section 4.6 during the 40-week Extension Period;
5. A female patient becomes pregnant during the study;
6. The patient fails to comply with protocol requirements or study-related procedures if, in the opinion of the Investigator or the Sponsor, the non-compliance will significantly compromise data interpretation or safety;
7. In the Investigator's judgment, it is in the patient's best interests;
8. Violation of the protocol inclusion and exclusion criteria is discovered, if, in the opinion of the Investigator or the Sponsor, the violation will significantly compromise data interpretation or safety;
9. The patient is unblinded during the 40-week Extension Period; or
10. The Sponsor or the regulatory authority terminates the study.

Patients who choose to withdraw consent will be asked to document withdrawal of consent in writing.

Although a patient is not obligated to give his/her reason for withdrawing prematurely, the Investigator will make a reasonable effort to obtain the reason while fully respecting the patient's rights. The reason for withdrawal from the study must be documented in the eCRF. The CSR will include the reason(s) withdrawal from the study.

If a patient withdraws prematurely from the study, study staff will make every effort to complete the full panel of assessments scheduled for the ET Visit.

If a patient withdraws from the study due to an AE, the patient will be asked to return to the site for, at a minimum, the evaluations scheduled for the ET Visit. If the AE has still not resolved, additional follow-up will be performed, as appropriate, and documented in the patient's medical records. As a minimum requirement, ongoing AEs are to be followed for 30 days after the patient's last dose of study drug. If patients are lost to follow-up, attempts to contact them must be made and documented in the study records. Withdrawn patients will not be replaced.

#### 4.5 RE-SCREENING OF SCREEN FAILURES

Patients who are screen failures, other than failing the TG criteria, can be re-screened once at a future date if they are then deemed eligible. Before each patient is re-screened, the Investigator should discuss the case with the Medical Monitor. It is acceptable to re-test only the out-of-range result, with the approval of the Medical Monitor.

Patients who were screen failures under the previous version of this protocol (Version 1.0) can be re-screened once again for this amended protocol (Version 2.0), only if the eligibility criteria determining the original screen failure have been revised in this amendment (for example, the criteria relating to eGFR, statin treatment, insulin treatment, [REDACTED] or blood pressure).

Patients who are screen failures only due to the eGFR criteria will undergo the following procedures:

- Patients with an eGFR <90 mL/min/1.73 m^2 but ≥30 mL/min/1.73 m^2 at Visit 1 will be screen failures for this study [REDACTED]  
[REDACTED]  
[REDACTED] and [REDACTED]
- Patients with an eGFR <30 mL/min/1.73 m^2, at Visit 1 will be screen failures.

---

#### **4.6 STUDY DRUG DISCONTINUATION FOR PERSISTENT ABNORMAL CLINICAL LABORATORY VALUES**

A patient will discontinue treatment with study drug if persistent elevations in ALT, AST, CK, or TG, or a persistent decrease in eGFR, occur according to the following criteria:

1. ALT or AST  $>8 \times$  ULN, confirmed on repeat;
2. ALT or AST  $>3 \times$  ULN and bilirubin  $>2 \times$  ULN or International Normalized Ratio (INR)  $>1.5$ , confirmed on repeat;
3. ALT or AST  $>3 \times$  ULN with the appearance of fatigue, nausea, vomiting, right upper quadrant pain or tenderness, fever, rash, and/or eosinophilia ( $>5\%$ ) confirmed on repeat;
4. ALT or AST  $>5 \times$  ULN which persists for 2 weeks;
5. Unexplained CK  $>5 \times$  ULN confirmed on repeat. For patients with CK  $\geq 10 \times$  ULN, Investigators should immediately interrupt study drug while awaiting re-evaluation;
6. Fasting TG levels  $>2000$  mg/dL (22.60 mmol/L) with signs or symptoms of pancreatitis at any time during the study. For repeated or persistent elevations of TG  $>2000$  mg/dL (22.60 mmol/L) that are not accompanied by signs or symptoms of pancreatitis, Investigators may discontinue study drug at their discretion; or
7. eGFR  $<30$  mL/min/1.73 m^2 occurring at or after Visit 7 (Week 12), confirmed on repeat.

If at any time during the study a patient develops elevations in ALT or AST  $>3 \times$  ULN, CK  $>5 \times$  ULN, TG  $>2000$  mg/dL ( $>22.60$  mmol/L), or a decrease in eGFR  $<30$  mL/min/1.73 m^2 at Visit 7 (Week 12) or any subsequent visit, the study site will receive an alert from the central laboratory.

For further details regarding study drug discontinuation for persistent abnormal clinical laboratory tests, see Section 5.2.2.

---

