#### 5.2.2.1 ***Liver Function Test Elevations***

With any of the following liver function test elevations, patients should undergo repeat laboratory measurements as soon as possible, preferably within 72 hours (unless otherwise specified), and no later than 1 week. Local laboratory measurements may be used to facilitate follow-up:

- ALT or AST  $>8 \times$  ULN;
- ALT or AST  $>3 \times$  ULN and bilirubin  $>2 \times$  ULN or INR  $>1.5 \times$  ULN;
- ALT or AST  $>3 \times$  ULN with the appearance of fatigue, nausea, vomiting, right upper quadrant pain or tenderness, fever, rash, and/or eosinophilia ( $>5\%$ ); and
- ALT or AST  $>5 \times$  ULN, regardless of symptoms should be followed up within 1 week.

Repeat evaluation should include AST, ALT, prothrombin time/INR, total bilirubin, alkaline phosphatase, gamma-glutamyltransferase, creatinine, CK, and complete viral hepatitis screen. The patient should be questioned regarding symptoms, as well as potential causative factors. This information, including results and normal ranges of any laboratory parameters collected at a local laboratory, should be collected on the appropriate eCRF. Hepatobiliary ultrasonography and/or consultation with a hepatologist should be considered if clinically indicated.

Abnormal laboratory parameters should be followed at least weekly (more frequently as clinically indicated) until they have returned to baseline or have stabilized.

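### The INR cut-off for stopping study drug (above 1.5, section 4.6) differs from the cut-off that triggers the timed repeat test (above 1.5 × ULN, section 5.2.2.1)

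*Protocol*

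**What the plan says.** Protocol section 4.6 lists the laboratory findings that end treatment. Criterion 2 combines ALT or AST above 3 × ULN with bilirubin above 2 × ULN or, for INR, "International Normalized Ratio (INR) $>1.5$ , confirmed on repeat". This INR limit is an absolute value. Criterion 2 sets no time for the repeat. Section 4.6 closes by sending the reader to section 5.2.2 for details.

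Section 5.2.2.1 lists the liver findings that call for repeat measurement, "preferably within 72 hours (unless otherwise specified), and no later than 1 week". Its second bullet uses the same ALT/AST and bilirubin limits as criterion 2, but its last part reads "ULN or INR $>1.5 \times$ ULN". This INR limit is relative to the laboratory's upper limit of normal.

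Section 5.2.2.1 then sets the work-up: "Repeat evaluation should include AST, ALT, prothrombin time/INR, total bilirubin, alkaline phosphatase, gamma-glutamyltransferase, creatinine, CK, and complete viral hepatitis screen". It ends with a general instruction: "Abnormal laboratory parameters should be followed at least weekly (more frequently as clinically indicated) until they have returned to baseline or have stabilized".

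Section 4.6 also provides a central-laboratory alert. For transaminases above 3 × ULN it applies without a visit limit: "If at any time during the study a patient develops elevations in ALT or AST".

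**The concern.** A repeat trigger should fire no later than the stopping rule that depends on the repeat. Here the order can be reversed. Where the laboratory's INR upper limit is above 1.0, the value that can stop treatment is lower than the value that prompts the timed confirmation. Nothing in either section explains a difference, and the rest of the two criteria match, so it looks like a drafting slip.

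At stake is the consistency of a liver-safety decision across about 200 planned sites. For a patient between the two cut-offs, one section makes a repeat decisive for stopping drug, while the section it points to does not list that patient among those who need the repeat. Section 5.2.2.1 also lets local laboratories be used for follow-up, so the relative cut-off can move with the laboratory while the stopping cut-off stays fixed.

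**Working it through.** **Inputs.** Stopping cut-off: INR above 1.5 (section 4.6, criterion 2). Repeat trigger: INR above 1.5 × ULN (section 5.2.2.1, second bullet). The INR ULN is not in the documents, so 1.0 to 1.3 is assumed as a range. The plan states no figure of its own to reproduce.

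**Step 1: width of the unmatched band.** Band = (1.5 × ULN) − 1.5.

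| Assumed INR ULN | Repeat trigger, 1.5 × ULN | Band above 1.5 |
|---|---|---|
| 1.0 | 1.50 | 0 |
| 1.1 | 1.65 | 0.15 |
| 1.2 | 1.80 | 0.30 |
| 1.3 | 1.95 | 0.45 |

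**Step 2: who falls in the band and meets no other trigger.** Taking the section 5.2.2.1 bullets in turn, the patient must have:

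- ALT and AST not above 8 × ULN (first bullet), and in fact not above 5 × ULN (fourth bullet), with at least one above 3 × ULN;
- bilirubin no more than 2 × ULN and INR no more than 1.5 × ULN (second bullet);
- none of the listed symptoms or signs and no eosinophilia above 5% (third bullet).

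The unmatched group is therefore ALT or AST above 3 and up to 5 × ULN, bilirubin at or below 2 × ULN, no listed symptom or eosinophilia, and INR above 1.5 but at or below 1.5 × ULN. Such a patient meets the values in criterion 2 of section 4.6 and no bullet in section 5.2.2.1.

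**Step 3: what this group lacks.** This depends on how the closing weekly sentence of section 5.2.2.1 is read.

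- If it covers every abnormal liver value, the outer limit is 7 days in both cases, a difference of 7 − 7 = 0. The preferred timing differs: 72 hours is 3 days, against 7 days, a difference of 4 days. The specified panel is also not triggered. It has nine items: AST, ALT, prothrombin time/INR, total bilirubin, alkaline phosphatase, gamma-glutamyltransferase, creatinine, CK and a viral hepatitis screen.
- If it covers only the bulleted elevations, the protocol sets no time for the repeat that decides whether drug is stopped.

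**The case against.** The strongest reply is that no patient escapes the safety rule. The lower cut-off belongs to the mandatory stopping rule, which itself demands confirmation, so a repeat follows whatever section 5.2.2.1 says. Everyone in the unmatched group has ALT or AST above 3 × ULN and so generates a site alert at any visit. The weekly sentence is not worded as limited to the bullets, and read naturally it supplies the 7-day limit. What is left is a preference for 72 hours and a recommended panel. In addition, the ULN is unknown, the gap vanishes at 1.0, and most exclusion criteria are redacted, so the number of patients affected cannot be estimated. All of this stands as a limit on the consequence. It does not make the two thresholds agree, and it relies on sites reconciling them.

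A reader might infer more: that patients in the band would stay on drug unchecked until the next scheduled draw. The documents do not support that, for the reasons just given.

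A reader might also see a parallel fault in the eGFR rules. Section 5.2.2.4 asks for a repeat of any eGFR below 30 without a visit limit, and chemistry is drawn at Week 4, yet the alert for eGFR applies "at Visit 7 (Week 12) or any subsequent visit, the study site will receive an alert from the central laboratory". This is not an error. Stopping criterion 7 has the same start, "occurring at or after Visit 7 (Week 12), confirmed on repeat", so the alert matches the rule it serves. Section 5.2.2.4 says should rather than must, and can be read as the procedure for that criterion. The Week 4 value is not hidden either: section 6.1 blinds key lipid results, and section 5.2.2 has the investigator or a delegated physician review and sign every laboratory report.

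**Conclusion.** The mismatch is real and can be read directly from the text: two sections that govern the same liver finding use different INR cut-offs. It has a practical effect only if the laboratory's INR upper limit exceeds 1.0. Over the assumed 1.1 to 1.3 the unmatched band is 0.15 to 0.45 INR units wide, and it applies to a narrow group whose size the documents do not allow us to estimate. On the more natural reading of the weekly sentence, the loss is the 72-hour preference and the nine-item panel. On the narrower reading, it is any stated time limit for the confirming test. Severity is minor. Sample size, type I error and the primary analysis are unaffected.

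**What to change.** In Protocol section 5.2.2.1, second bullet, change the INR limit from 1.5 × ULN to an absolute 1.5, to match criterion 2 of section 4.6. Changing the trigger rather than the stopping rule keeps the more protective value and removes the dependence on each laboratory's range.

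The cost is one wording edit and a few more unscheduled repeat tests, with no added scheduled visits or samples. The SAP introduction reports that the study is finished and the database locked, so the correction now serves any later protocol that reuses this wording.

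As an optional extra, not a correction, the sponsor could extend the eGFR alert to Week 4. The Week 12 start of the eGFR stopping criterion can stay as it is.

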#### 5.2.2.2 *Creatine Kinase Elevations*

In the event of a CK elevation  $>5 \times$  ULN, the patient should return to the site within 1 week for evaluation.

For a CK elevation  $>10 \times$  ULN, study drug should be interrupted immediately while awaiting evaluation.

Evaluation should include the patient being questioned about symptoms (e.g., muscle or tendinous pain, cramping, or weakness) and potential causes for the CK elevation (e.g., medications, exercise, or trauma). The following laboratory measurements should be obtained: CK, CK-MB, CK-MM, troponin, creatinine, myoglobin (serum and urine), transaminases, total bilirubin, and urinalysis including urine sediment. A physical examination should be performed, documenting findings such as muscle tenderness, weakness, or rash. An ECG should be collected as well. This information should be collected on the appropriate eCRF. For abnormalities to be reported as AEs, see Appendix D for a list of muscle AE definitions.

Abnormalities should be followed until they have returned to baseline, or the Investigator considers them clinically stable.

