#### 5.2.2.3 *Triglyceride Elevations*

For alerts due to fasting TG levels  $>2000$  mg/dL (22.60 mmol/L), the patient should return to the site within 1 week for clinical and laboratory assessments. Patients should be assessed for potential signs or symptoms of pancreatitis (including measurements of serum amylase and lipase), and a repeat assessment of fasting TG will be obtained. For patients with asymptomatic elevations of TG, compliance with study drug and lifestyle recommendations should be assessed and reinforced. Patients should be closely followed for the emergence of signs and symptoms of pancreatitis until TG levels are  $<2000$  mg/dL (22.60 mmol/L). If 2 consecutive alerts for a patient are sent due to elevated TG levels  $>2000$  mg/dL (22.60 mmol/L), the Investigator may contact the Medical Monitor to discuss study drug discontinuation and further monitoring.

To maintain the integrity of the blind, TG values from post-randomization blood samples obtained prior to Visit 8 (Week 16), run by the central laboratory, will not be communicated to the sites (see Section 6.6).

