#### **5.2.2.4 *Estimated Glomerular Filtration Rate Decrease***

For eGFR <30 mL/min/1.73 m^2, the patient should return to the site within 1 week for repeat laboratory assessment. Abnormal laboratory parameters should be followed at least weekly (more frequently as clinically indicated) until they have returned to baseline or have stabilized.

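### The central-laboratory alert for eGFR <30 starts only at Week 12, so it misses the on-treatment Week 4 sample, for which the protocol already requires recall

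*Protocol*

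**What the plan says.** Section 4.6 of the protocol lists seven laboratory findings that end study-drug treatment, and then says which results make the central laboratory alert the site.

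- **Stopping.** Criterion 7, eGFR below 30 mL/min/1.73 m², counts only when "occurring at or after Visit 7 (Week 12), confirmed on repeat". The other six criteria carry no visit limit.
- **Alert.** The sentence opens with "If at any time during the study a patient develops elevations in ALT or AST" and treats CK and TG on the same footing. For eGFR it narrows to a decrease "at Visit 7 (Week 12) or any subsequent visit, the study site will receive an alert from the central laboratory".

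Section 4.6 then points onward: "For further details regarding study drug discontinuation for persistent abnormal clinical laboratory tests, see Section 5.2.2". For an eGFR below 30, Section 5.2.2.4 says "the patient should return to the site within 1 week for repeat laboratory assessment", and adds: "Abnormal laboratory parameters should be followed at least weekly (more frequently as clinically indicated) until they have returned to baseline or have stabilized". It sets no visit limit.

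Study drug starts on Day 1 (Section 7.5.1). Serum chemistry is drawn at Visit 5, Week 4 (Table 2; Section 6.3). eGFR is in that panel (Section 5.2.2), and Appendix A lists it without a visit restriction, whereas lipase and amylase are restricted to Visits 1 and 4.

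**The concern.** The two rules do not match. The duty to recall a patient begins with any eGFR below 30, but the signal that tells the site one has occurred begins only at Week 12. At Week 4 the site has to find the value itself when it reads the report. ALT/AST, CK and TG results at the same visit would each raise an alert.

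This is a matter of patient safety only. If the report were read late or the value overlooked, a large loss of renal function in the first weeks of treatment could go without the required recall until the next scheduled eGFR. No data monitoring committee is planned (Section 5.4), so prompt recognition rests with the site.

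**Working it through.** The plan states no figure to reproduce. The check sets the provisions side by side, with a little arithmetic on timing and size.

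**1. Which on-treatment samples does the alert miss?** Section 6.3 schedules on-treatment chemistry at Weeks 4, 12, 16, 28, 40 and 52. Visit 6 (Week 8) has lipids but no chemistry. The eGFR alert covers Week 12 onward, so Week 4 is the one scheduled on-treatment eGFR outside it.

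**2. What applies to a Week 4 eGFR below 30?**

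| Provision | Applies at Week 4? |
|---|---|
| Central-laboratory alert (4.6) | No |
| Mandatory stop once confirmed (4.6, criterion 7) | No |
| Recall within 1 week, then at least weekly follow-up (5.2.2.4) | Yes |
| Physician evaluation and signing of every laboratory report (5.2.2) | Yes |
| Discretionary stop for an AE or in the patient's interest (4.3, reasons 3 and 6) | Yes |
| Interruption for an AE, with restart allowed (4.3) | Yes |

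The recall rule applies, but its automatic prompt does not.

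**3. Time to the next scheduled eGFR.** Week 12 − Week 4 = 8 weeks, or 84 − 28 = 56 days. Each visit has a ±3-day window, so the range is (84 − 3) − (28 + 3) = 50 days to (84 + 3) − (28 − 3) = 62 days.

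**4. Difference in the date of a mandatory stop, if criterion 7 also covered Week 4.** With equal repeat lags the difference is again 56 days (50 to 62 with the windows). Section 5.2.2.4 allows the repeat at any time within 1 week, so each lag can be 0 to 7 days and the range widens to 50 − 7 = 43 days up to 62 + 7 = 69 days. This compares two dates on which stopping becomes compulsory. It is not a delay in detecting the fall.

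**5. How large a fall is needed?** Under Section 4.5, an eGFR below 90 at Visit 1 is a screen failure. From exactly 90, reaching 30 is a fall of (90 − 30)/90 = 66.7%. A value below 30 needs more than that, and a higher starting value needs more still. The documents give no event rate, and none is assumed here.

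**The case against.** The strongest defence is that the Week 12 limit is deliberate. It appears twice in Section 4.6, so it is unlikely to be a slip, and Visit 7 is when fenofibrate enters the trial. Section 1.2 says that fibrates generally call for caution when renal function is impaired and expects fewer such restrictions for K-877. The visible text does not give this as the reason, and parts of the protocol are redacted, but the timing fits.

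A reader might answer that the rule cannot be about fenofibrate, because from Week 12 it also binds K-877 patients, whose K-877 dose does not change. That does not follow. The Extension Period is double-blind, so a stop meant for fenofibrate would have to apply to both arms.

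A reader might also infer that Section 5.2.2.4 is defective because it names no study-drug action. The neighbouring subsections do not support that. Only the CK text is directive: "study drug should be interrupted immediately while awaiting evaluation". The TG text is permissive: "the Investigator may contact the Medical Monitor to discuss study drug discontinuation and further monitoring". The liver subsection (5.2.2.1) names no study-drug action and closes its follow-up in the same way.

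The Week 4 safeguards are also substantial. Besides those in the table, Section 9.1 makes an abnormal result an AE if, for example, it comes with symptoms or changes dosing. A fall of more than two-thirds would be hard to miss when a report is signed.

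These arguments carry weight against extending the mandatory stop. They do not explain why the alert is withheld. An alert commits nobody to stopping drug, and it would serve a recall rule that the protocol already applies at every visit.

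**Conclusion.** The point holds for the alert, as a minor inconsistency within the protocol. Section 5.2.2.4 requires recall for a Week 4 eGFR below 30, and Section 4.6 withholds the automatic prompt. The exposure is one scheduled sample per patient, with about 8 weeks to the next, and the event should be very rare. That expectation rests on the entry limit of 90 at Visit 1, not on an event rate. The primary endpoint, the testing hierarchy and the efficacy analyses are untouched.

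Two stronger readings are not supported. One is that a patient with a Week 4 eGFR below 30 would be left unmanaged on study drug until Week 12. Report review, recall, weekly follow-up, interruption and discretionary stopping all apply before then. The other is that the missing mandatory stop is itself an error. The Week 12 start may be tied to fenofibrate, and leaving the earlier decision to the Investigator is a defensible choice. The wording is certain. The reason behind the limit is not, because the public text does not state it.

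**What to change.** In the alert sentence of Section 4.6, delete the phrase restricting eGFR to Visit 7 or later, so that the alert covers every post-randomization eGFR below 30, including Week 4. This brings it into line with the other analytes in that sentence and with Section 5.2.2.4. At the protocol stage the cost is one wording deletion, one alert setting at the central laboratory and a rare extra alert, with no new tests or visits. The SAP introduction reports that the study has finished, so the change has value as a protocol-stage correction only.

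Extending criterion 7 to before Week 12 is optional and has a real downside. Section 4.3 does not let a patient restart after discontinuation but does allow restart after an interruption for an AE. A mandatory stop would remove that option for a reversible acute cause, in placebo patients as well as K-877 patients. If it were adopted, Section 4.3 keeps such patients in the study to Week 12, so the primary endpoint could still be measured. If the limit on stopping is kept, one sentence giving the reason would settle the question.
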